12.3 EXCLUSION CRITERIA

Participants who meet any of the following criteria will be excluded from participating in this study:

- 1. Are in a current state of mania, as determined by the YMRS or psychosis, as determined by the MINI.
- 2. Are diagnosed with vitamin or hormonal deficiencies that may mimic mood disorders, as determined by the investigator.
- 3. Are currently receiving any other interventional therapy for MDD other than a stable regimen of antidepressants or psychotherapy as defined in the inclusion criteria.
- 4. Considered to have treatment resistant depression as defined by inadequate clinical response to 2 or more trials of antidepressants at an adequate dose and duration.
- 5. Have a history of electroconvulsive therapy (ECT), transcranial magnetic stimulation (TMS), cranial electrotherapy stimulation (CES), transcranial direct current stimulation (tDCS), deep brain stimulation (DBS), or other brain stimulation.
- 6. Patient answers Yes to Questions 4, 5 or 6 on the Columbia Suicide Severity Rating Scale (C-SSRS) Triage and Risk Identification Screener.
- 7. Any previous hospitilization for suicidal behavior.
- 8. Have chronic severe insomnia (< 4 hours of sleep each night), or depression secondary to chronic insomnia or sleep apnea
- 9. Have any structural lesion (e.g., any structural neurological condition, or more subcortical lesions than would be expected for age or have had a stroke that affects stimulated area or connected areas) or any other clinically significant abnormality that might affect safety, study participation, or confound interpretation of study results, as determined by the investigator.
- 10. Have any implant in the brain (e.g., DBS) or neurocranium, or any other active implantable medical device.
- 11. Have any neurocranial defect.
- 12. Have a history of epilepsy or seizures (including history of withdrawal / provoked seizures).
- 13. Have shrapnel or any ferromagnetic material in the head.
- 14. Have any disorder that would impair the ability to complete the study questionnaires.
- 15. Have been diagnosed with autism spectrum disorder.
- 16. Are actively abusing substances (<1 week prior to enrollment).
- 17. Have a cognitive impairment (including dementia).
- 18. Have a history of mania or psychosis.
- 19. Are currently using any medications that affect cortical excitability (e.g., benzodiazepines, epileptics, etc.).
- 20. Are currently experiencing symptoms of withdrawal from alcohol or benzodiazepines.
- 21. Have been diagnosed with Parkinsonism or other movement disorder as determined by the investigator to interfere with treatment.
- 22. Have ever taken esketamine / ketamine for treatment of depression.
- 23. Have ever been admitted to hospital for depression.
- 24. Have ever been diagnosed with obsessive-compulsive disorder (OCD) or bipolar type 1 or 2 disorder.
- 25. Is diagnosed with an active primary anxiety disorder, or PTSD, agoraphobia, anorexia or bulimia, panic or personality disorder with active symptoms.
- 26. Have a history of psychosurgery for depression.
- 27. Have any history of myocardial infarction, coronary artery bypass graft (CABG), coronary heart failure (CHF), or history of other cardiac issues.
- 28. Are currently experiencing or have a history of intractable migraines.
- 29. Are a chronic tobacco smoker, as defined by smoking by smoking >100 cigarettes (including hand-rolled cigarettes, cigars, cigarillos, etc.) in their life-time and have smoked every day for the last 7 days.

- 30. If female and of child-bearing potential, currently pregnant or breastfeeding or planning to become pregnant or breastfeed any time during the study.
- 31. Are currently a prisoner.
- 32. Are participating concurrently in another clinical investigation or have participated in a clinical investigation within the last 90 days or intend to Participate in another clinical investigation during the study, and where the participation in the other investigation might interfere with the results of this trial as deemed by the PI.
- 33. Have any medical condition or other circumstances, in the judgment of the investigator, that might interfere with the ability to complete follow-up visits and the self-reported MADRS-s in the app.
- 34. Have any condition which, in the judgment of the Investigator, would preclude adequate evaluation of the device's safety and performance.
- 35. A Subject who meets any of the exclusion criteria during study participation will be discontinued from the study

12.4 Study Enrollment Procedures

All participants with MDD will be considered for screening into the study. Participants expressing an interest in participation will proceed with the consent process as per section 13.1 Informed Consent. A participant is not considered officially enrolled in the study until after signing the study consent form.

12.4.1 PARTICIPANT ENROLLMENT

Participants who consent to participate shall be assigned a unique Participant Identification Number to de-identify their information. This Participant Identification Number will be captured in the Curebase platform and used to identify them on all source documents and eCRFs thereafter.

A record of all screened participants will be maintained in the Curebase platform. The date of screening, results of screening (included or not) and, if not eligible, the primary reason for excluding the participant, enrollment status (enrolled or not) and, if not enrolled, the primary reason will be recorded.

Please note, for purposes of the study a participant is considered enrolled at informed consent.

NOTE: If a participant does not meet the eligibility criteria during their initial screening, the participant cannot be re-evaluated for entry into the study later.

12.5 SCREEN FAILURES

A screen failure participant is a consented participant that did not receive the Flow FL-100 treatment due to withdrawing consent, being withdrawn from the study, or not meeting eligibility requirements for treatment.

If a participant signs the ICF but is found ineligible for inclusion in the study prior to receiving the Flow FL-100, the participant will not be advanced any further in this clinical investigation. The participant's signed ICF and completed inclusion/exclusion criteria will be retained by the Investigator, and the participant will be notified.

Screening data from the Screening Visit including the reason for exclusion, will be collected but may not be complete in cases where the participant is determined to be a screen failure early in the screening process. The participant's exclusion from the study, and reason for ineligibility, will be documented in the Screening & Enrollment Log.

12.6 PARTICIPANT TREATMENT ASSIGNMENT

During the technical onboarding session at Week 0, the participant will receive the link to the app and a code to access the app. The participant will download the app and sign up in the app with their email, password, and app access code. When the participant creates their account in the trial app they will automatically be randomized to the sham or active treatment arm (with 50% probability). Block randomization is used with randomly permuted block sizes of 4 and 6. This is done by the trial server and stored in its dedicated database. No one who is working with the trial will have access to the raw data until it has ended.

13 STUDY PROCEDURES

13.1 WEEK -3 TO -1: INFORMED CONSENT (ICF)

After passing the screener survey, prospective participants will be directed to review and sign an electronic HIPAA, and an IRB/EC-approved consent (eConsent) form that are hosted in the Curebase system. The eConsent form will explain the nature and scope of the study, the procedures to be performed as part of the study, the potential risks, and benefits of participation, expected duration of participation, possible treatment alternatives, and an overview of his/her rights as a study participant in lay terms. Participants will have the opportunity to discuss the study with their family or surrogates or think about it before agreeing to participate. Participants will be informed that participation is voluntary and will be assured that they may withdraw from the study at any time and for any reason, without repercussion.

After viewing the eConsent materials, participants will have an opportunity to email or call the research team with any questions they may have and will be given as much time as needed to receive answers before making a final decision regarding study participation. Participants will receive a telephone number, email, and will have access to contact support staff as needed.

When the individual is ready to confirm their willingness to participate, an electronic signature will be collected to complete the eConsent formalities. The participant will receive a copy of the fully signed HIPAA, and eConsent forms via email to retain for their records, and a digital copy will be retained within the Curebase system as part of the study records.

Upon successful documentation of informed consent, a screening video call will be performed and will serve as a baseline evaluation to confirm patient eligibility.

- Clinician Reported Outcome (ClinRO)
 - Hamilton Depression Rating Score (HDRS-17)
 - Montgomery–Åsberg Depression Rating Scale (MADRS)
 - Mini International Neuropsychiatric Interview (MINI)
 - Hamilton Anxiety Rating Scale (HAM-A)
 - Young Mania Rating Scale (YMRS)
 - Rey Auditory Verbal Learning Test (RAVLT)
- Patient Reported Outcome (PRO) Questionnaires
 - EQ-5D-3L
 - Symbol-Digit Modalities Test (SDMT)
 - Treatment Acceptability Questionnaire (TAQ)
 - tDCS Adverse Events Questionnaire (AEQ)
 - Columbia Suicide Severity Rating Scale (C-SSRS)
- Review of concomitant medications
- Final review of inclusion/exclusion criteria
- Intervention kit will be shipped to the participant

13.2 WEEK 0

To allow the Investigator's assessment of the participant's progress, the participant will complete a video call with study staff and undergo the following:

- Review of concomitant medications
- Record any new or updated adverse events and device deficiencies, if applicable
- SDMT baseline
- Technical onboarding & device training session
- Randomization

13.3 WEEKS 1, 4 & 7

To allow the Investigator's assessment of the participant's progress, the participant will complete a video call with study staff and undergo the following:

- ClinROs
 - HDRS-17

- MADRS
- YMRS
- C-SSRS
- Review of concomitant medications
- Record any new or updated adverse events and device deficiencies, if applicable

13.4 WEEK 10

To allow the Investigator's assessment of the participant's progress, the participant will complete a video call with study staff and undergo the following:

- ClinROs/PROs
 - HDRS-17
 - MADRS
 - HAM-A
 - YMRS
 - EQ-5D-3L
 - RAVLT
 - SDMT
 - TAQ
 - AEQ
 - C-SSRS
- Review of concomitant medications
- Record any new or updated adverse events and device deficiencies, if applicable

For participants in the Sham Arm:

• Participants in the Sham arm will be informed of their assignment and will be offered to start active, Open-Label stimulation for 10 weeks, with 5 sessions the first 3 weeks and then up to 3 sessions per week.

For participants in the Active stimulation Arm:

- Participants in the Active arm will be offered to continue maintenance treatment for 10 more weeks at 3 sessions per week.
- 13.5 WEEK 20 FOLLOW-UP VISIT OPEN-LABEL ONLY

To allow the Investigator's assessment of the participant's progress, the participant will complete a video call with study staff and undergo the following:

- ClinROs/PROs
 - HDRS-17
 - MADRS
 - HAM-A
 - YMRS
 - EQ-5D-3L
 - RAVLT
 - SDMT
 - TAQ
 - AEQ
 - C-SSRS
- Review of concomitant medications
- Record any new or updated adverse events and device deficiencies, if applicable.

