7 SCHEDULE OF PROCEDURES

Table 1. Schedule of Procedures. Activities in blue cells are performed by trained graduate researchers supervised by a trained psychiatrist, and red cells are to be completed by the participant.

	Pre-Treatme nt		E	Blinded Pha	ise		Open-La Phas	abel e	Early termination ⁸
Activity	Week -3 to -1 (± 3 days)	Week 0	Week 1 (± 3 days)	Week 4 (± 3 days)	Week 7 (± 3 days)	Week 10 (± 3 days) Final blinded visit ¹	Week 10 (± 3 days) Open Label Start	Wee k 20 (± 3 days)	Week 1-20
Informed Consent	х								
Screening and baseline Video Call	х								
Diagnostic Assessment for MDD	X٩								
Intervention Kit Shipped to subject	X ⁵								
Randomization ⁶		Х							
Technical onboarding		х							
Initial Visit		Х							
Video call	Х	Х	Х	Х	Х	Х		Х	Х
MINI	Х								
HDRS-17	X		X	Х	X	X		X	X
MADRS	Х		Х	Х	Х	Х		X	Х
MADRS-s	X	X ⁴	X	X	X	X		X	Х
C-SSRS	X		X X	X X	X X	X		X	X X
YMRS	X X		X	X	X	X X		X	X
HAM-A	X					X		X X	X
EQ-5D-3L RAVLT	X					X		X	X
SDMT	~	X ²				 X ²		Λ X ²	^
TAQ	X	~				X		X	Х
AEQ						X		X	X
Healthcare Visit Survey ³						X		X	X
FLOW FL-100 use ⁷		х	х	х	х	х	х	Х	
Record/Review Concomitant Medications	х	х	х	х	х	х		х	х
Record/Review Adverse Events		Х	Х	Х	Х	Х		Х	Х

CA-127-T1, v3.0 Flow Neuroscience AB, FL001 CONFIDENTIAL Page **19** of **69**

¹ The week 10 visit includes the study Primary end-point. This will be the final blinded visit and will be the start of the open label phase of the study. Participants in the Sham arm will be informed of their assignment and will restart with active stimulation for 10 weeks; participants in the Flow FL-100 arm will be allowed to continue maintenance treatment for 10 more weeks at 3 sessions per week. The unblinding will occur after the primary end-point data has been recorded. ² Optional

³ Participants will be surveyed about the number of times he/she has sought healthcare due to depression during the previous 10 weeks.

⁴ Participants will be required to answer the nine questions of the MADRS-s form in the app to start the first stimulation session during the technical onboarding.

⁵ Participants will be required to start treatment within 24 days from completing the baseline surveys.

⁶ Completed after eligibility is confirmed by the investigator; when the participant signs up with their email in the trial app they will automatically be randomized to the sham or active treatment arm (with 50% probability).

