22.4 RANDOMIZATION

After a subject has met all inclusion criteria and none of the exclusion criteria, and creates an account in the Flow app, the subject will be randomized. Randomization will be performed in a 1:1 ratio to the Active and Sham groups. Randomization will be performed using randomly permuted block sizes of 4 and 6 and done independently for the two sites.

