22.11 EVALUATION OF BLINDING

An evaluation of blinding will be performed. Prior to subjects unblinding through the system they will respond to the question "Which treatment arm do you think you are in?" (answers: sham/active), followed by the question "How certain are you of this?", with the options 1 to 5 where 5 is very certain and 1 is very uncertain. The counts and percentages of the subjects responding correctly will be tabulated and reported.

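### Section 13.4 attaches arm disclosure to the Week 10 rating call, one participant at a time, and no rule keeps raters unaware of earlier participants' arms

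*Protocol*

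**What the plan says.** Section 13.4 (Week 10) describes a visit in which "the participant will complete a video call with study staff and undergo the following". HDRS-17 and MADRS head the list. Under the same visit come two arm-specific items: "Participants in the Sham arm will be informed of their assignment and will be offered to start active" treatment, and "Participants in the Active arm will be offered to continue maintenance treatment for 10 more weeks at 3 sessions per week".

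On who rates, the Table 1 legend in section 7 says "Activities in blue cells are performed by trained graduate researchers supervised by a trained psychiatrist". The cell colours are not visible in the text at hand, but no separate masked rater is named anywhere.

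On timing and route, footnote 1 to Table 1 says "The unblinding will occur after the primary end-point data has been recorded". Section 22.11 says "Prior to subjects unblinding through the system they will respond to the question" on which arm they believe they are in. That question goes to participants only.

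On allocation, section 22.4 says "Randomization will be performed using randomly permuted block sizes of 4 and 6 and done independently for the two sites", in a 1:1 ratio. Section 12.6 places the assignment on the trial server and adds "No one who is working with the trial will have access to the raw data until it has ended".

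Two further places bear on what staff can see. Table 3 gives former sham participants 5 sessions a week for the first three open-label weeks, against 3 for former active participants. Section 8.3 says trial personnel can see which participant used which device, and when.

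**The concern.** The primary endpoint is a clinician rating, so the double-blind claim depends on the rater as much as on the participant. Footnote 1 protects each participant's own rating from that participant's own unblinding. It does nothing for the next participant in the same block.

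Section 13.4 reads as a staff-visit procedure and section 22.11 as a system procedure. Even disclosure through the app alone would leave the arm legible from the open-label schedule and the device log.

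If raters accumulate knowledge of earlier arms, balanced blocks turn it into information about participants still to be rated. A rater who leans with the guess would bias HDRS-17 and MADRS. The planned blinding evaluation could not show it, because raters are never asked.

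**Working it through.** **The plan's own figures.** The protocol gives no figure for predictability. Its sample size supplies the yardstick of 3.2 points, and it reproduces. The pooled SD is √((7.1² + 7.9²)/2) = 7.51. A two-sample t-test at one-sided 0.025 needs 88 per arm (176 in all, power 80.2%). With 108 per arm the power is 87.6%, and 216/0.8 = 270.

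**Inputs from the protocol.** 270 participants at two sites capped at 155 each (section 6), so 115 to 155 per site, 135 if equal. Enrolment of about 5 months (11.1), Week 10 window of ±3 days (Table 1), blocks of 4 and 6 by site (22.4), 20% attrition (22.2).

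**Assumptions.** Uniform accrual over 150 days, block sizes equally likely, Week 10 at day 70, visits spread evenly over the window, and attrition meaning that the arm is never disclosed. The number of raters per site is not stated, so it is varied.

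**Timing.** At 135/150 = 0.9 participants a day, a block of 6 fills in about 6/0.9 = 6.7 days, long before its first disclosure at about day 70. Knowledge of a block therefore arrives too late to affect entry, and it hardly touches the ratings at Weeks 1, 4 and 7. It does arrive in time for Week 10: after the first participant at a site, virtually everyone is rated after some disclosure there.

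**Accuracy of the guess (chance is 50%), 135 per site, by simulation.** The simple rule guesses the arm less often disclosed so far. The best guess uses the full randomisation order and the block structure.

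| Situation | Simple rule | Best guess |
|---|---|---|
| One rater, all disclosed, no visit spread | 69% | 69% |
| One rater, all disclosed, ±3 days | 65–66% | 68–69% |
| One rater, 20% never disclosed, ±3 days | 55% | 63% |
| Two raters, no sharing, ±3 days | 52–53% | 58–59% |
| Two raters, no sharing, 20% never disclosed, ±3 days | 52% | 56–57% |

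Across 115 to 155 per site, the one-rater best guess stays at 68–70% with full disclosure and at 63–64% with 20% never disclosed. The arm is certain for about 5–11% of participants with full disclosure and about 1–4% with 20% never disclosed.

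**Role of the printed block sizes.** With full disclosure in randomisation order, a guesser who ignores the sizes is right 69.0% of the time, and one who uses them 69.1%. In the other rows, the gap between the columns also reflects tracking the whole randomisation order, so it does not measure the effect of printing the sizes.

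**Bias in the arm difference.** Suppose a rater scores L/2 lower when guessing active and L/2 higher when guessing sham. With accuracy p, the arm difference shifts by L × (2p − 1). For L = 1 point:

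- p = 0.52: 0.04 points (0.04/3.2 = 1% of the planned effect)
- p = 0.55: 0.10 points (3%)
- p = 0.64: 0.28 points (9%)
- p = 0.69: 0.38 points (12%)

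The shift is proportional to L, which has no source in the protocol.

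**The case against.** The strongest objection is that no sentence says the rater hears the arm. Section 13.4 is in the passive voice and lists the offers after the assessments. Section 22.11 routes unblinding through the system, and section 12.6 keeps the list on the server. This stands: that raters learn arms is an inference from the shared call, and the defect is the missing safeguard together with the two descriptions of the route.

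The higher accuracies also need a single rater per site who sees every disclosure. The protocol plans for 20% attrition and speaks of researchers in the plural. With either feature the simple rule falls to 52–55%. This stands as well, and the range has to be reported.

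Three stronger readings are tempting and not supported:

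- **Section 12.6 is contradicted.** It restricts access to raw data. A participant learning their own arm through the app leaves that sentence true.
- **Printing the block sizes creates the problem.** Mixed-size permuted blocks run centrally are ordinary practice, and with full disclosure in order the sizes add 0.1 percentage points to accuracy.
- **Allocation concealment at entry fails.** Disclosure comes about ten weeks after a block has been filled.

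What the objection does not answer is that nothing shields a rater from earlier arms, whichever route is used.

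**Conclusion.** The point holds as a gap in rater blinding at Week 10. As written, 13.4 ties disclosure and arm-specific offers to the call containing the primary rating. It does so while other participants at the site are still to be rated, and it does not match 22.11.

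Prediction is probabilistic: about 65–69% right with one rater per site and full disclosure, and about 52–64% with 20% attrition or several raters who do not share information. The resulting bias is conditional on an assumed lean. For 1 point in total it is roughly 0.05–0.4 points against 3.2, and it is zero if raters do not lean. The protocol does not show that raters will be unblinded or that bias will occur. It shows that nothing prevents either, and that the planned blinding check would not reveal it. Correction is worthwhile because the endpoint is clinician-rated and the remedy is cheap.

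**What to change.** 1. In section 13.4 and footnote 1 to Table 1, align with 22.11: deliver disclosure and the arm-specific offer only through the app, after the Week 10 ratings are recorded and outside the rating call.
2. State that staff who rate HDRS-17 and MADRS have no view of any participant's open-label arm, schedule or device-use log until the last Week 10 rating at that site is locked.
3. Instruct participants not to reveal their arm to raters.
4. Add to 22.11 a rater arm-guess at Week 10, recorded before that participant's disclosure.

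If raters learn no arms before the site's last Week 10 rating, guessing from the blocks returns to 50%. Removing the block sizes from the protocol or rewording 12.6 is not needed for this.

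The cost is protocol wording, an app message, restricted system views and one extra question, with no added visits or staff. Questions about the open-label offer would go to app or technical support instead of the rater. Raters at Week 20 may still hear some arms from participants, including while others at the site await Week 10, so the instruction in item 3 reduces the leak without closing it.
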